**Table 5.2 Dose Modifications and Dosing Delays**

Dose Level	Osimertinib (PO daily) Each Cycle 28 Days
0	80 mg
-1	40 mg

Treatment or visit delays for public holidays or weather conditions do not constitute a protocol violation.

The following dose modification rules will be used with respect to potential toxicity. Toxicity will be assessed according to the NCI CTCAE Version 4.03.

If a patient experiences a CTCAE grade 3 or higher and/or unacceptable toxicity including a DLT, not attributable to the disease or disease-related processes under investigation, dosing will be interrupted and supportive therapy administered as required in accordance with local practice/guidelines.

If toxicities do not resolve to less than or equal to Grade 2 after 2 weeks despite supportive care, then the participant should be withdrawn from the study.

**Table 5.3 Dose Modifications and Dosing Delays Tables for General Adverse Events**

Grade of Event	Management/Next Dose for Osimertinib
≤ Grade 1	No change in dose
Grade 2	Hold until ≤Grade 1 if clinically significant, otherwise no change in dose Resume at same dose level
Grade 3	Hold* until <Grade 2 Resume at one dose level lower, if indicated**
Grade 4	Off protocol therapy

\*Patients requiring a delay of >2 weeks should go off protocol therapy

\*\*Patients who do not tolerate 40 mg PO daily dose will be taken off protocol therapy

\*\*\*Alopecia/hair color changes are excluded from requirement for dose delays or modifications

## Dose Modifications and Dosing Delays Tables for Specific Adverse Events

**Table 5.4 Adverse Event: Diarrhea**

Grade of Event	Management/Next Dose for Osimertinib
≤ Grade 1	No change in dose
Grade 2	Hold until ≤Grade 1 if clinically significant, otherwise no change in dose Resume at same dose level
Grade 3	Hold* until ≤Grade 2 Resume at one dose level lower**
Grade 4	Off protocol therapy

Recommended management: Loperamide antidiarrheal therapy, see section 5.3.1

\*Patients requiring a delay of >2 weeks should go off protocol therapy

\*\*Patients who do not tolerate 40 mg PO daily dose will be taken off protocol therapy

**Table 5.5 Adverse Event: Pulmonary/Cardiac Toxicity**

PULMONARY	
Notes:	

 
Withhold osimertinib for acute onset of new or progressive unexplained pulmonary symptoms, such as dyspnea, cough and fever and during diagnostic workup for pneumonitis/ILD.
 
During evaluation of potential grade 2, 3, and 4 pneumonitis, if an infectious etiology is confirmed (i.e., pneumonia) and pneumonitis is excluded, then consider resuming at current dose level after the pneumonia resolves.
 
	
ILD/Pneumonitis	
Grade of Event	Dose Modifications for osimertinib
Grade 1 or greater	Permanently discontinue osimertinib
CARDIAC INVESTIGATIONS	
Abnormal LVEF	
Symptomatic congestive heart failure or asymptomatic left ventricular systolic dysfunction which persists for $\geq 4$ weeks	Permanently discontinue osimertinib
Electrocardiogram QT corrected (QTc) interval prolonged***	
Grade 1 (QTc 450-480 ms)	Maintain dose level
Grade 2 (QTc 481-500 ms)	
Grade 3 (QTc $\geq 501$ ms)	
 
Perform an analysis of serum potassium, magnesium, calcium, and phosphorus, and if below lower limit of normal, correct with supplements to within normal limits. Review concomitant medication uses for an agent which may cause prolonged QTc and discontinue if clinically feasible.
 
Hold osimertinib until QTc is less than 481 ms or to baseline if baseline is <math>>481</math> ms, then resume treatment, with osimertinib dose- if recovery within 3 weeks of onset, then restart at a reduced (40 mg) or at 80 mg (at the discretion of the investigator).* If QTc prolongation recurs patient will be permanently discontinued from the study.
 
Repeat ECG in 24 hours, or less, as clinically indicated; continue monitoring as clinically indicated until QTc <math><481</math> ms.
 
Repeat ECGs 7 days after dose resumption for all patients who had therapy interrupted due to QTc <math>\geq 501</math> ms.
 

Grade 4 (QTc $\geq 501$ or $>60$ ms change from baseline and Torsades de pointes or polymorphic ventricular tachycardia or signs/symptoms of serious arrhythmia)	Permanently discontinue patient from study
*Patients requiring a delay of $>2$ weeks should go off protocol therapy	
**Patients who do not tolerate dose level -1 dosing should go off protocol therapy	
***QTc prolongation as confirmed on three separate ECGs	

**Table 5.6 Adverse Event: Dermatologic**

Grade of Event	Management/Next Dose
≤ Grade 1	No change in dose
Grade 2	No change in dose
Grade 3	Hold* until <Grade 2 Resume at one dose level lower
Grade 4	Hold* until <Grade 2 Resume at one dose level lower

Please see Section 5.3.1 for recommendations regarding supportive care to be undertaken in patients experiencing dermatologic AEs on study

\*Patients requiring a delay of >2 weeks should go off protocol therapy

\*\*Patients who do not tolerate dose level -1 dosing should go off protocol therapy

### 5.3 Monitoring and Toxicity Management

Each patient receiving osimertinib will be evaluable for safety. The safety parameters include all laboratory tests and hematological abnormalities, physical findings, ECG findings, echocardiography findings, and spontaneous reports of AEs reported to the investigator by patients.

Each patient will be assessed periodically for the development of any toxicity as outlined in Section 6 Study Procedures and Observations. Toxicity will be assessed according to the NCI CTCAE v4.03. Dose adjustments will be made according to the system showing the greatest degree of toxicity.

We will monitor for potential adverse effects including but not limited to fatigue, nausea, vomiting, dehydration, cytopenias, and signs and symptoms of infection. In addition we will monitor specifically for the following AEs of special interest (Please see the corresponding subsections in Section 6.2 for acute toxicity management and dose modifications).

- Rash/Dry Skin
- Diarrhea
- Ejection Fraction Changes
- Prolonged QTc
- Pneumonitis/ILD
- Liver Chemistry Elevations
- Hyperglycemia

Management of any grade 3 or higher toxicity should be discussed with the PI of the study.

#### 5.3.1 Other toxicities

Toxicity will be managed according to local guidelines.

#### Rash and Dry Skin

Rash, acneiform rash, and dry skin are common AEs experienced on osimertinib therapy. The following guidelines are provided to facilitate supportive care in patients experiencing these findings. These skin adverse effects may occur at any time but are most likely to start within two weeks of starting treatment.

We recommend application of over-the-counter moisturizing cream to face, hands, and feet twice daily from the start of treatment with osimertinib.

For **Grade 1 or 2 rash and acne** we recommend initiation of emollient cream and/or a topical moderate strength steroid BID and/or a topical antibiotic BID. For **grade 2 rash/acne**, a six-week course of oral antibiotics can be considered. For **grade 3 or greater rash/acne**, we recommend a topical moderate strength antibiotic BID in combination with a 6-week course of oral antibiotic.

For **grade 1 or 2 dry skin** consider over the counter moisturizing cream or ointment BID to face/hands/feet with ammonium lactate 12% cream or salicylic acid 6% cream BID to the body. For **grade 3 or greater dry skin** add a topical moderate strength steroid to eczematous areas of the body.

For patients experiencing **grade 1 pruritus** consider a topical moderate strength steroid or topical antipruritic BID to localized areas. For patients with **grade 2 pruritus** consider an oral antihistamine. For **grade 3 or greater pruritus**, consider addition of a GABA agonist (such as gabapentin).

### Diarrhea

Initiate dietetic measures including discontinuing lactose-containing products, frequent small meals, increased fluid intake with 8 to 10 glasses of clear liquids per day, and a low fat regimen enriched with rice, bananas, and applesauce.

For **grade 1 or 2 diarrhea**, initiate pharmacologic treatment with loperamide as per the following dosage schedule: Loperamide 4 mg at first onset, followed by 2 mg with each loose motion until diarrhea-free for 12 hours (maximum dosage 16 mg/24 hours). Grade 1 intermittent diarrhea may not require treatment. Adjunct anti-diarrheal therapy is permitted and should be recorded when used. Use electrolyte replacement as appropriate. In patients with **≥ grade 3 diarrhea**, consider IV fluids and more frequent electrolyte monitoring as indicated, with consideration for prophylactic antibiotics if diarrhea is persistent beyond 24 hours, there is fever, or **≥ grade 3 neutropenia**.

### Left Ventricle Ejection Fraction Changes

Osimertinib and its active metabolites may inhibit HER2 and a low rate of LVEF decrease from baseline has been reported in patients treated with osimertinib. Patients will be evaluated for abnormal LVEF at baseline. Subsequently, measurement of LVEF should be performed if the investigator has clinical suspicion of new onset impaired cardiac function. Patients are to be managed clinically according to standard of care, with cardiologic consultation at the investigator's discretion. Patients with asymptomatic reduction in LVEF which persists for greater than 4 weeks, or with symptomatic congestive heart failure, should permanently discontinue treatment with osimertinib.

### **Pneumonitis/ILD**

Pneumonitis/ILD can occur in patients treated with osimertinib. Patients with new or worsening dyspnea, cough, or new pulmonary radiological abnormality while receiving treatment, without clinically evident alternative etiology, should hold osimertinib, undergo a high resolution CT scan of the chest and the investigator should be notified. It is strongly recommended to perform a full diagnostic workup, to exclude alternative causes such as lymphangitic carcinomatosis, infection, allergy, cardiogenic edema or pulmonary hemorrhage. The results of full diagnostic workup (including high-resolution computed tomography (HRCT), blood and sputum culture, haematological parameters) will be captured by eCRF. In the presence of confirmatory HRCT scans where other causes of respiratory symptoms have been excluded, a diagnosis of interstitial lung disease should be considered and study treatment permanently discontinued.

Where ILD is suspected, administer corticosteroids at a dose of 1 to 2 mg/kg/day prednisone equivalents for Grade 2 or greater pneumonitis, followed by corticosteroid taper. Permanently discontinue osimertinib for any grade ILD/pneumonitis.

### **Liver Chemistry Elevations**

Patients with combined increases in transaminases (AST or ALT to greater than 3x the ULN) and total bilirubin (to greater than 2x the ULN) should be reviewed for compatibility with Hy's law (Appendix 7). An appropriate diagnostic evaluation for alternative etiologies should be completed within a three-week period. Patients with both an increased in AST or ALT to greater than 3x the ULN AND subsequent or coincident elevation in total bilirubin to greater than 2x ULN, without an alternative explanation upon clinical evaluation (i.e. cholestasis, viral hepatitis, another drug exposure), are found to meet the criteria for Hy's Law and should be reported as an SAE.

### **Hyperglycemia**

Treatment with osimertinib may result in hyperglycemia in some patients, most commonly in the first week of treatment. Regular monitoring of fasting or non-fasting blood glucose (FBG) will be completed as described in the study procedures in section 6.1. If a patient has a non-fasting glucose level of  $> 140$  mg/dL (ULN for glucose within 2 hours of eating), then they must have a fasting glucose drawn and followed with fasting glucose for all future monitoring. Investigators should use discretion on an individual patient basis regarding need for more frequent monitoring: for example, patients with pre-existing diabetes or glucose intolerance. These patients should perform home monitoring at least once weekly during the first two cycles of treatment. Patients should be educated to contact the site if they have any positive urine glucose test or a home blood glucose reading of  $>160$  mg/dL ( $>8.9$  mmol/L) and any time they experience symptoms that have correlated with osimertinib-induced hyperglycemia, including increases in nausea, vomiting, anorexia, diarrhea, fatigue, polydipsia, polyuria, and polyphagia. Upon reports of positive home tests and/or symptoms suggesting hyperglycemia, local laboratory FBG tests should be performed.

The following guidelines serve as recommended management guidelines for hyperglycemia; however, management of individual patients is deferred to the treating physician's judgement.

**Table 5.7 Management Guidelines for Hyperglycemia**

FBG Result	Antihyperglycemic Interventiona	Osimertinib Dose Modification
Grade 2 (>160 to 250 mg/dL; >8.9 to 13.9 mmol/L)	
 
If asymptomatic,b repeat test within 1 week; if results in this range at least twice in 1 week, start antihyperglycemicc and continue home monitoring;
 
If symptomatic,b start antihyperglycemic and continue home monitoring.
 
	
 
Osimertinib may continue without interruption or dose reduction.
 

Grade 3 (>250 to 500 mg/dL; >13.9 to 27.8 mmol/L)	
 
Start antihyperglycemic and continue home monitoring.
 
	
 
If asymptomatic,b osimertinib may continue without interruption or dose reduction;
 
If symptomatic,b interrupt osimertinib until resolution/improvement in symptoms and FBG <250 mg/dL (<13.9 mmol/L).c
 

Grade 4 (>500 mg/dL; >27.8 mmol/L)	
 
Start antihyperglycemic and continue home monitoring.
 
Consider adding a second antihyperglycemic agent.d
 
	
 
Interrupt osimertinib dosing until resolution/improvement in symptoms and FBG <250 mg/dL (<13.9 mmol/L).c
 

FBG, fasting blood glucose

a Oral antihyperglycemic agent (e.g., metformin), which may need to be maintained for duration of osimertinib treatment. Use of insulin or agents that increase insulin production (e.g., sulphonyl ureas) is generally not recommended because the mechanism of osimertinib-induced hyperglycemia is not due to a deficit in insulin production.

b Increased nausea, vomiting, anorexia, diarrhea, and fatigue have been most common symptoms of hyperglycemia.

c Per Investigator discretion, osimertinib may be restarted at the same dose. A reduced dose may also be considered if glucose levels prove difficult to control.

d Additional anti-hyperglycemia agents such as SGLT2 inhibitors (e.g., dapagliflozin) or pioglitazone, which increase glucose uptake or increase glucose excretion, may be added to metformin.

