### 3.4 Duration of Therapy

Patients may receive up to 2 cycles of therapy prior to surgery. Surgery must occur within 14 days of final scans. Patients will continue the study drug following final scans and then discontinue the study drug between 3 and 7 days prior to surgery, and thus may ultimately receive up to two weeks additional therapy with study drug beyond end of cycle 1 (or cycle 2) while awaiting surgery. No treatment with the study drug will be given after surgery.

Criteria for treatment with Cycle #2:

- No Grade 3 or higher AEs with Cycle #1
- No evidence of PD by RECIST 1.1 criteria at end of Cycle #1 scan.
- Additional reduction in tumor size deemed to be potentially beneficial by thoracic surgeon planning to perform resection.

Treatment may be stopped for any of the following reasons:

- The patient or legally authorized representative withdraws consent.
- Any AE that in the opinion of the investigator would pose an unacceptable safety risk to the patient.
- Closure of the study.

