## 5.2 Dose Modifications and Dosing Delays

If a patient experiences a CTCAE grade 3 or higher and/or unacceptable toxicity including a DLT, not attributable to the disease or disease-related processes under investigation, dosing will be interrupted and supportive therapy administered as required in accordance with local practice/guidelines.

If a toxicity resolves or reverts to  $\leq$ CTCAE grade 2 within 3 weeks of onset, treatment with osimertinib may be restarted at the same dose (80 mg) or a lower dose (40 mg) using the rules below for dose modifications (Table 5.2) and with discussion and agreement with Principal Investigator (PI). There will be no individual modifications to dosing schedule in response to toxicity, only potential dose reduction or dose interruption.

On resolution of toxicity within 3 weeks: If an AE subsequently requires dose interruption, osimertinib may restart at the same dose or the reduced dose, on resolution/improvement of the AE at the discretion of the Investigator.

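### Sections 5.2 and 5.3.1 give incompatible dosing instructions for asymptomatic grade 3 and for grade 4 hyperglycemia, and nothing says which governs

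*Combined protocol and SAP*

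**What the plan says.** Section 5.2 opens with a general rule. Its trigger is "If a patient experiences a CTCAE grade 3 or higher and/or unacceptable toxicity including a DLT", provided that the toxicity is not attributable to the disease, and its action is "dosing will be interrupted and supportive therapy administered as required in accordance with local practice/guidelines". The rule is repeated under Table 5.2 and has no exception for any event. The same section allows a restart at 80 mg or 40 mg once the toxicity is back to grade 2 or lower within 3 weeks, with no separate treatment of grade 4.

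Table 5.3, for general adverse events, holds at grade 3 until below grade 2. At grade 4 its entry is "Off protocol therapy". Its only stated exclusion is alopecia and hair color changes. Tables 5.4 to 5.6 then follow under a heading for specific adverse events; hyperglycemia is not among them.

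Hyperglycemia appears later, in section 5.3.1, with its own Table 5.7. For asymptomatic grade 3 (fasting glucose >250 to 500 mg/dL) the dose-modification column repeats its grade 2 instruction, "Osimertinib may continue without interruption or dose reduction". For symptomatic grade 3, and for grade 4 (>500 mg/dL), it interrupts until symptoms improve and fasting glucose is below 250 mg/dL. Footnote c adds: "Per Investigator discretion, osimertinib may be restarted at the same dose". The introduction to the table calls it recommended and says "management of individual patients is deferred to the treating physician's judgement".

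Section 3.4 lists among the conditions for a second cycle: "No Grade 3 or higher AEs with Cycle #1".

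**The concern.** Hyperglycemia is one of the adverse events of special interest listed in section 5.3. For an asymptomatic grade 3 value, a site cannot follow both a rule that interrupts dosing and a table that lets it continue. For a grade 4 value, one table ends protocol therapy while another table and the general text leave a restart open.

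What is at stake is first the clarity of a safety instruction. In a multi-site trial it also touches consistency: whether continued dosing is compliant or a protocol violation depends on which provision an auditor applies, and exposure before resection could differ between sites for the same glucose value.

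**Working it through.** The plan states no figure on this point, so the check is a side-by-side reading, followed by a rough count.

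**Step 1: action by grade**

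| Glucose event | Section 5.2 text | Table 5.3 | Table 5.7 | Result |
|---|---|---|---|---|
| Grade 3, asymptomatic | Interrupt | Hold until below grade 2 | Continue, no reduction | Conflict |
| Grade 3, symptomatic | Interrupt | Hold until below grade 2 | Interrupt until symptoms improve and fasting glucose <250 mg/dL | Agreement on interruption; recovery thresholds differ |
| Grade 4 | Interrupt; restart at 80 or 40 mg if grade 2 or lower within 3 weeks | Off protocol therapy | Interrupt; footnote c allows restart at the same dose or consideration of a reduced one | Table 5.3 conflicts with both others |

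The grade 4 clash is therefore mainly inside section 5.2. Its own text allows restart where its own Table 5.3 ends treatment, and this applies to any general grade 4 event. Table 5.7 sides with the section 5.2 text on this.

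**Step 2: is there a precedence rule?**

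- No sentence says that Table 5.7 overrides section 5.2 or Table 5.3, or the reverse.
- Section 5.3 lists hyperglycemia and sends the reader to event subsections for dose modifications, but gives their location as Section 6.2. Section 6.2 covers specimen acquisition.
- The section 5.3 sentence on adjusting to the system with the greatest toxicity concerns toxicity in several systems. It does not rank two rules for one event.
- Section 5.3.1 does link QTc prolongation to Table 5.5. No such link joins section 5.2 to Table 5.7.

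**Step 3: the Cycle 2 criterion**

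Section 7.3.1 defines an adverse event broadly enough to include an abnormal laboratory finding. Its paragraph on examinations and tests then says that deterioration in protocol-mandated laboratory values should be reported as an adverse event only if it meets a seriousness criterion or is the reason for discontinuing treatment. Glucose is in the mandated chemistry panel (section 6.1; Appendix 1, footnote 7). Whether an asymptomatic grade 3 glucose, with dosing continued under Table 5.7, counts under section 3.4 cannot be settled from the text.

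**Step 4: rough size**

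Table 4.4 does not list hyperglycemia, and the documents give no rate elsewhere. Assume 1% to 5% of patients reach grade 3 or higher:

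- 27 × 0.01 = 0.27
- 27 × 0.05 = 1.35

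That is about 0.3 to 1.4 of 27 patients. The count includes symptomatic grade 3 cases, where all rules interrupt, so fewer fall in the conflicting rows.

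**The case against.** The best reply is that the specific rule displaces the general one. Table 5.3 is labelled general, and the event tables openly depart from it: Table 5.6 allows resumption after a grade 4 dermatologic event, and Table 5.5 stops treatment for grade 1 pneumonitis. The events listed in section 5.3 match the subsections of 5.3.1, so the intended target of the wrong cross-reference is easy to guess, and Table 5.7 has a column for osimertinib dose modification. Section 5.3 also asks that any grade 3 or higher toxicity be discussed with the study PI, which gives sites a common decision-maker.

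Much of this stands as evidence of intent. It does not amount to a stated rule. Table 5.7 lies outside the group of specific-event tables in section 5.2. None of the tables in that group lets dosing continue through a grade 3 event. A table offered as a recommendation, subject to physician judgement, does not plainly displace an instruction worded as mandatory. Discussion with the PI softens the risk but gives neither the PI nor an auditor a written rule.

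Two stronger readings are tempting. A reader might infer that one patient could be continued, interrupted or taken off therapy depending on the page consulted. The table above does not support that: no single grade carries all three initial actions, Table 5.3 ends therapy by grade only at grade 4, and Table 5.7 never continues dosing at grade 4. A reader might also infer that section 3.4 bars a second cycle after a grade 3 glucose that Table 5.7 handled without a dose change. The laboratory reporting rule in section 7.3.1 leaves that open.

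**Conclusion.** The contradiction is real but narrow. Asymptomatic grade 3 hyperglycemia is to be interrupted under section 5.2 and held under Table 5.3, yet may continue under Table 5.7. Grade 4 hyperglycemia ends protocol therapy under Table 5.3, yet may be followed by restart under the section 5.2 text and footnote c of Table 5.7. There is no conflict on interruption for symptomatic grade 3. A specific-over-general intent is plausible but unstated.

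The number affected is unknown and probably about one patient or fewer; that estimate rests entirely on the assumed 1-5% rate. A reader might go on to infer a distorted MPR result. The documents show no such effect, and the case for amending rests on clear safety instructions and consistent handling. It should be corrected because sites cannot follow both rules for a listed event of special interest and the correction is cheap.

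**What to change.** By amendment:

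1. Reconcile the general rule in section 5.2 and Table 5.3 with Table 5.7, and state which governs hyperglycemia at grade 3 (asymptomatic and symptomatic) and at grade 4. This could be done by moving hyperglycemia into the specific-event tables with an explicit override, or by aligning Table 5.7 with the general rule.
2. Reconcile the grade 4 entry of Table 5.3 with the restart text of section 5.2, since that mismatch reaches beyond hyperglycemia.
3. Correct the cross-reference in section 5.3 that now points to Section 6.2.
4. State, in light of the laboratory reporting rule in section 7.3.1, whether an asymptomatic grade 3 glucose counts as an adverse event for the Cycle 2 criterion in section 3.4.

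Which clinical rule applies is for the sponsor's clinicians; this review takes no position. The cost is amendment wording, with no extra procedures and no change to sample size or analysis.
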